9.7.5. Months 1, 2 Procedures

- Perform a physical examination.
- Assess and record AEs
- Review and record prior and concomitant medications.
- Assess investigational product compliance, perform investigational product accountability, and review dosing diary with the subject.
- Obtain blood samples for serum chemistry, hematology, and coagulation tests.
- Perform assessments for calculation of Child-Pugh Score.
- Review progression to cirrhosis algorithm.
- Provide the subject with a dosing diary to document his or her dosing.
- In the event it is not feasible for the subject to return to the site for the above referenced procedures, the following alternative visit procedures are available to help ensure compliance with the Month 1 and Month 2 visit laboratory requirements:
 - At the Day 0 visit, the subject can be provided with the central laboratory collection kit and shipping materials associated with the Month 1 visit, and have the laboratory specimen collection performed at his or her local doctor's office or designated laboratory collection center. The subject must also be contacted via telephone at the visit timepoint to assess AEs, review concomitant medications, and assess investigational product compliance;
 - If all other options for the collection of the Month 1 and Month 2 laboratory samples have been exhausted, the use of a local laboratory for the Month 1 samples would be accepted for this visit; although, any laboratory data obtained from a local laboratory will not be captured in the eCRF or included in the study analysis. A copy of the local laboratory report would need to be provided to the Investigator for review and available in the source records. The Investigator should contact the Medical Monitor as soon as possible to discuss any local laboratory values that may be of clinical concern. The subject must also be contacted via telephone at the visit timepoint to assess AEs, review concomitant medications, and assess investigational product compliance;

- A physical examination should be performed at the Month 3 visit if an onsite Month 1 or Month 2 visit was not performed.
- Schedule the next visit, reiterate dosing instructions, and advise the subject:
 - NOT to take investigational product on the morning of the next visit, and
 - To bring the investigational product bottle(s); s/he will dose at the clinic (if this is in compliance with the established dosing frequency), and
 - To fast overnight (at least 8 hours) prior to the next visit. Fasting is required prior to all study visits, but water is permitted.

9.7.6. Month 3 Procedures

- Perform assessments for calculation of Child-Pugh Score.
- Review progression to cirrhosis algorithm
- Assess and record vital signs (weight, temperature, sitting heart rate, respiratory rate, and sitting blood pressure).
- Assess and record AEs.
- Review and record prior and concomitant medications.
- Review and record any non-study related medical or surgical treatment procedures and any medically relevant HCP or non-HCP related office visits that have occurred since the previous study visit.
- Assess investigational product compliance, perform investigational product accountability, and review dosing diary with the subject.
- Assess for dose titration, if eligible (refer to [Section 7.4](#)).
- Verify that the subject has fasted for at least 8 hours.
 - Record fasting status in the source and CRF
 - If the subject reports having eaten within 8 hours, document accordingly in the source and CRF and remind the subject that fasting is required prior to all study visits, but water is permitted.
- Obtain blood samples for serum chemistry, hematology, and coagulation tests.
- Obtain blood samples for:
 - OCA, C4, and FGF-19
- Assess the subject's supply of investigational product to ensure an adequate amount. Access the IWRS and dispense investigational product if necessary.
- Provide the subject with a dosing diary to document his or her dosing.
- Schedule the next visit, reiterate dosing instructions, and advise the subject:
 - NOT to take investigational product on the morning of the next visit, and

- To bring the investigational product bottle(s); s/he will dose at the clinic (if this is in compliance with the established dosing frequency), and
- To fast overnight (at least 8 hours) prior to the next visit. Fasting is required prior to all study visits, but water is permitted.

9.7.7. Post-Titration Visit Procedures

- Perform a physical examination.
- Assess and record AEs.
- Review and record prior and concomitant medications
- Assess investigational product compliance, perform investigational product accountability, and review dosing diary with the subject.
- Obtain blood samples for serum chemistry, hematology, and coagulation tests.
- Perform assessments for calculation of Child-Pugh Score.
- Review progression to cirrhosis algorithm
- Provide the subject with a dosing diary to document his or her dosing.
- In the event it is not feasible for the subject to return the site for the above referenced procedures, the following alternative visit procedures are available, to help ensure compliance with the Post-Titration laboratory requirements:
 - At the Up-titration Visit, the subject can be provided with the central laboratory collection kit and shipping materials associated with the Post-Titration Visit, and have the laboratory specimen collection performed at his or her local doctor's office or designated laboratory collection center. The subject must also be contacted via telephone at the Post-Titration Visit timepoint to assess AEs, review concomitant medications, and assess investigational product compliance;
 - If all other options for the collection of the Post-Titration laboratory samples have been exhausted, the use of a local laboratory for the Post-Titration samples would be accepted for this visit; although, any laboratory data obtained from a local laboratory will not be captured in the eCRF or included in the study analysis. A copy of the local laboratory report would need to be provided to the Investigator for review and available in the source records. The Investigator should contact the Medical Monitor as soon as possible to discuss any local laboratory values that may be of clinical concern. The subject must also be contacted via telephone at the Post-Titration Visit timepoint to assess AEs, review concomitant medications, and assess investigational product compliance;
 - A physical examination should be performed at the next scheduled visit if an onsite Post-Titration Visit was not performed
- Schedule the next visit, reiterate dosing instructions, and advise the subject:
 - NOT to take investigational product on the morning of the next visit, and

- To bring the investigational product bottle(s); s/he will dose at the clinic (if this is in compliance with the established dosing frequency), and
- To fast overnight (at least 8 hours) prior to the next visit. Fasting is required prior to all study visits, but water is permitted.

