7.4.1. Pre-Titration Tolerability Assessment Requirements

Tolerability of investigational product must be assessed prior to titrating a subject to a higher dose. A review of adverse events and safety laboratory results (eg, chemistry, hematology, and coagulation) obtained within 2 months of the up-titration visit must be performed as part of the investigational product tolerability assessment, prior to any planned up-titration in investigative product (eg, Month 3, Month 6). Safety laboratory results obtained at the Month 1 visit (for titration at Month 3) or at the Post-Titration Assessment visits (for titration prior to or at the

subsequent quarterly visit) are acceptable for review purposes; however, if for any reason, laboratory results are not available at the time of the planned up-titration visit, additional laboratory samples must be obtained and reviewed, prior to up-titrating the subject to a higher dose.

To be eligible for a dose up-titration:

- Subjects should not be experiencing significant AEs that are suspected to be related to investigational product (eg, severe pruritus) or displaying other symptoms that may indicate intolerability of investigational product.
- There must be no clinically significant increase (as determined by the Investigator) in the subject's liver function tests.

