- Unscheduled visits as needed in the event of signs or symptoms of suspected hepatic injury or decompensation or if laboratory alerts have been triggered

It is important that the laboratory assessments be completed as required and that the central laboratory be used for assessments whenever possible. In the event that a subject cannot return to the clinic for a scheduled or unscheduled visit, or there is an event that triggers a need for an immediate assessment, the use of a local lab is permissible at the discretion of the Investigator. In these cases, the Investigator will obtain the laboratory results and the laboratory normal ranges.

The process for assessing criteria is presented in Figure 2, and the specific threshold(s) for each laboratory analyte to trigger mandatory repeat testing and, potentially a complete subject evaluation (depending on the repeat result) are summarized in Table 4.

Figure 2: DILI Management Algorithm

IP: Investigational Product

DILI = drug-induced liver injury; IP = Investigational Product

Note: Other laboratory criteria include: ALT, AST, total bilirubin, INR, and electrolytes (sodium).

Table 4: Liver Laboratory Criteria for Monitoring of Suspected Hepatic Injury or Potential Hepatic Decompensation and Criteria for Interruption or Discontinuation of Investigational Product

A. Laboratory Criteria for Monitoring Suspected Hepatic Injury		
Laboratory Parameter	Action Taken	Rechallenging Criteria
Total Bilirubin		If a subject interrupts IP, they may be rechallenged after a minimum of 30 days if fully resolved OR stable and approved by the Medical Monitor and Investigator.
Baseline \leq ULN and \geq 3x baseline	Interrupt IP	
Baseline $>$ ULN and \geq 2x Baseline	Interrupt IP	
ALT or AST		
$>$ 3x baseline (and $>$ ULN)	Interrupt IP	
\geq 2x baseline	Repeat Test in 2 to 3 days, interrupt IP if still elevated	
Electrolytes^a		
Sodium $<$ 130 mEq/L	Repeat Test in 2 to 3 days, interrupt IP if still below threshold	
B. Laboratory Criteria for Monitoring Potential Hepatic Decompensation (Absence of Clinical Symptoms)		
Total Bilirubin	Closely monitor until normalization or stabilization.	The subject may be rechallenged after a minimum of 30 days if fully resolved OR stable and approved by the Medical Monitor and Investigator.
Baseline \leq ULN and 1.5 mg/dL increase from baseline	If values continue to increase relative to the baseline value, interrupt IP.	If laboratory values do not normalize, IP should not be restarted.

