12.1.10. Follow-Up of AEs and SAEs

All AEs must be followed during the course of the study until the AE resolves, is no longer of clinical concern, has stabilized or is otherwise explained, or the subject is lost to follow-up.

AEs ongoing at the final visit that are deemed to be “possibly, probably, or definitely” related or of other clinical significance must be followed for as long as necessary to adequately evaluate the safety of the subject or until the event stabilizes, resolves, or is no longer of clinical concern. If resolved, a resolution date for the AE should be documented on the eCRF. The Investigator must ensure that follow-up includes any supplemental investigations indicated to elucidate the nature and/or causality of the AE. This may include additional laboratory tests or investigations, or consultation with other healthcare professionals, as considered clinically appropriate by the Investigator.

Drug-Induced Liver Injury or Disease Progression

All subjects showing possible drug-induced liver injury should be followed until all abnormalities return to normal or to the baseline state. Drug-induced liver injury may develop or progress even after the causative drug has been stopped. Results from drug-induced liver injury follow-up should be recorded in the eCRF. Note that longer follow-up can sometimes reveal an off-drug repetition of what had appeared to be drug-induced liver injury, indicating that liver injury was related to underlying liver disease.

Cholecystitis or Pancreatitis

At the time of consent for new subjects (or re-consent to the protocol amendments for ongoing subjects), subjects will be instructed to contact the investigational site if they experience any of the following signs and symptoms: nausea, vomiting, abdominal pain, diarrhea, weight loss, fever and chills, worsening or new fatigue, or weakness. Subjects will also be counseled to seek immediate medical assistance if they experience persistent severe abdominal pain.

In the event that cholecystitis and/or pancreatitis is suspected, Investigators will be instructed to promptly bring subjects into the clinic to undergo a complete evaluation, including a physical examination, and laboratory assessments [ie, amylase and lipase]). Investigators should refer to standard of care guidelines on suspected pancreatitis ([Banks 2012](#), [Greenburg 2015](#)). Diagnosis of acute pancreatitis includes 2 of the following:

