Serum Chemistry	Albumin, blood urea nitrogen (BUN), creatinine, direct bilirubin, total bilirubin, aspartate aminotransferase [AST, SGOT], alanine aminotransferase [ALT, SGPT], ALP, GGT, electrolytes [calcium, chloride, potassium, sodium], glucose, total protein, and blood lipids (total cholesterol, LDL, HDL and very low-density lipoprotein [VLDL] fractions and triglycerides [TG]), magnesium, phosphorus, bicarbonate, unconjugated (indirect) bilirubin, conjugated (direct) bilirubin, free fatty acids
Hematology	Hemoglobin, hematocrit, white blood count with differential, neutrophils, lymphocytes, monocytes, eosinophils, basophils, platelets, red blood cell count (including MCV, MCH, MCHC)
Coagulation	Prothrombin time (PT), partial thromboplastin time (PTT), international normalized ratio (INR)
Urinalysis	pH, specific gravity, total protein, glucose, ketones, bilirubin, blood, microscopic exam, urobilinogen, albumin, creatine, leucocytes, nitrates, albumin/creatinine ratio (if positive)
Markers of Cholecystitis and Pancreatitis	amylase and lipase
Biomarkers of Hepatic Fibrosis and/or Inflammation	IgM, C-reactive protein (CRP), TNF- α , FGF-19, CK-18, ELF, and others as determined during course of study
Genetics	DNA including single-nucleotide polymorphisms (SNPs) that may be involved in PBC; RNA
Other	OCA (parent and conjugates [glyco and tauro], OCA-glucuronide) and C4

The Investigator should manage subjects with clinically significant lipoprotein abnormalities using local standard of care procedures as appropriate after assessing the individual subject's total cardiovascular risk profile.

Urine-based β -hCG pregnancy tests will be performed in female subjects of childbearing potential per protocol specified visits. If a urine pregnancy test is positive, a serum pregnancy test must be performed to confirm the result. If positive, the Sponsor must be notified and the subject will be followed, as outlined in [Section 12.1.11](#) through pregnancy outcome.

MELD scores and Child-Pugh score will be calculated at screening, and at all visits based on serum chemistry and coagulation.

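### Local laboratory results from the Month 1, Month 2 and post-titration visits are barred from the eCRF and the analysis, although Section 7.4.1 lets some of them support a dose increase

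*Protocol*

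**What the plan says.** Sections 9.7.5 and 9.7.7 of the protocol provide for subjects who cannot come to the site at Month 1, Month 2 or a post-titration visit. The first alternative is a central laboratory kit drawn elsewhere. Only when nothing else is possible may a local laboratory be used; in Section 9.7.5, "the use of a local laboratory for the Month 1 samples would be accepted for this visit". Both sections then say that "any laboratory data obtained from a local laboratory will not be captured in the eCRF or included in the study analysis". The result still reaches the investigator: "A copy of the local laboratory report would need to be provided to the Investigator for review and available in the source records". Values of clinical concern go to the Medical Monitor.

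Section 7.4.1 makes a review of adverse events and of safety laboratory results from the preceding 2 months a condition of any planned up-titration. It names "Safety laboratory results obtained at the Month 1 visit (for titration at Month 3) or at the Post-Titration Assessment visits" as usable for that review and does not say that they must come from the central laboratory.

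Three other sections bear on the point:
- Section 7.5.2 also permits local testing. It adds "In these cases, the Investigator will obtain the laboratory results and the laboratory normal ranges" and states no eCRF bar.
- Section 13.2.2 plans by-visit summaries of central laboratory data.
- Section 13.3 lists clinical laboratory results among the data that the DMC reviews.

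**The concern.** Hepatic injury and decompensation are a leading safety concern of this trial (Sections 5.6, 5.7 and 7.5). The visits under the bar hold the only scheduled liver tests between Day 0 and Month 3, and between an up-titration at Month 3 and the Month 6 visit. Those are the periods just after first exposure and just after a dose increase.

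A bilirubin, ALT or INR measured locally in these periods can inform the decision to continue or raise the dose, and can set off the Table 4 actions. The number itself never becomes trial data. A statistical analysis plan cannot bring it back, because the rule acts at data capture and not at analysis. The DMC would likewise not see it as laboratory data. Section 12.1.6 cites the DMC's roughly quarterly review of all safety and efficacy data as part of the reason for not expediting reports of suspected liver outcome events.

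**Working it through.** The plan gives no figure to reproduce. The check has three parts.

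**1. Which dose decisions can rest on a barred result?** Sections 7.4.1 and 7.3 (Table 3) read together:
- *Month 1*: named in Section 7.4.1 for titration at Month 3. This applies on both regimens.
- *Month 2*: not named in Section 7.4.1, although its local results fall under the bar in Section 9.7.5.
- *Post-titration*: named in Section 7.4.1 for a later increase. The standard regimen has only one planned increase (Table 3 shows none after 10 mg daily). In practice this means the second titration on the modified regimen (Child-Pugh B or C), or some re-escalations after a reduction. On the standard regimen, Section 7.3 waives the laboratory review when the reduction lasted less than 3 months.

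**2. At how many scheduled draws could the bar apply?** The inputs are quarterly visits (Tables 1 and 2), about 6 years of minimum follow-up (Section 7.1.3), draws at Months 1 and 2, and two post-titration draws per qualifying up-titration.

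Quarterly draws: 6 × 4 = 24.

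| Course | Draws under the bar | All post-baseline draws | Share |
|---|---|---|---|
| No up-titration | 2 (M1, M2) | 24 + 2 = 26 | 7.7% |
| Standard, up-titrated at M3 | 4 (M1, M2, M4, M5) | 24 + 4 = 28 | 14.3% |
| Modified, up-titrated at M3 and M6 | 6 (M1, M2, M4, M5, M7, M8) | 24 + 6 = 30 | 20.0% |

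The last row is a maximum, since Appendix A lets some 2-month post-titration visits merge with a quarterly visit. The shares fall with longer follow-up. Over 10 years there are 10 × 4 = 40 quarterly draws, giving 2/42 = 4.8%, 4/44 = 9.1% and 6/46 = 13.0%. They are higher early on: with an up-titration at Month 3, four of the six post-baseline draws to Month 6 fall under the bar.

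These are draws where the bar *could* apply. They are not data lost. The protocol gives no expected share of local samples, so the number of lost values cannot be derived.

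**3. What happens to one affected subject?** Take an up-titration at Month 3, every barred draw done locally, and no unscheduled central sample.
- All draws captured: months 0, 1, 2, 3, 4, 5, 6. Largest gap 1 month.
- Barred draws removed: months 0, 3, 6. Largest gap 3 months.

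The acceptance clause in Section 9.7.5 literally names only the Month 1 samples. If Month 2 is then always central, the captured draws in the first window are months 0, 2, 3, with a largest gap of 2 months. The gap after up-titration stays at 3 months.

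**The case against.** The case for leaving the text alone is substantial.

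*The sections do not contradict each other.* A reader might infer that 7.4.1 conflicts with 9.7.5 and 9.7.7. It does not. Section 7.4.1 governs the investigator's clinical review, and the other two send the local report to the investigator for that purpose. This stands: the gap is in data capture, not in the dosing decision.

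*The values do not support starting treatment.* Dosing begins on Day 1, after the Screening and Day 0 draws. This stands: they can bear only on continuing or raising the dose.

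*A result that supports an increase should be unremarkable.* Section 7.4.1 bars up-titration after a clinically significant rise in liver tests. A worrying value goes to the Medical Monitor and can be recorded as an adverse event, and a lasting rise would show at the next central draw. This limits the harm. It does not supply the values needed to describe liver tests soon after dosing or a dose change.

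*MELD events need not be lost.* Because "MELD scores and Child-Pugh score will be calculated at screening, and at all visits based on serum chemistry and coagulation", a reader might infer that a MELD component of the primary endpoint could be missed. The documents do not support that. They do not say that MELD must be derived from eCRF data, and adjudication under Section 13.4 works from available source documentation, which includes the retained report.

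*The bar is confined to two sections.* Sections 7.5.2 and 7.7 also allow local testing but contain no exclusion. Section 12.1.10 says "Results from drug-induced liver injury follow-up should be recorded in the eCRF", which meets the bar only if one of these visits is also injury follow-up. This stands, so the change belongs in 9.7.5 and 9.7.7 alone.

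*Central data are better standardised.* True, and a reason to flag local values and keep them out of the by-visit statistics. It is not a reason to leave them uncollected.

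**Conclusion.** The point holds as a minor one. The current text of Sections 9.7.5 and 9.7.7 states an exclusion rule that, followed as written, leaves some hepatic safety values out of the database and out of the laboratory data reaching the DMC. Section 7.4.1 allows some of those same values to support a dose increase: Month 1 for the Month 3 step, and post-titration mainly for the second step on the modified regimen.

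The effect on an affected subject is a gap between captured liver tests of up to 3 months in place of 1. That assumes both visits in the window are local and no unscheduled central sample is taken. The overall size is unknown and probably small, because local use is a last resort. The 8%, 14% and 20% shares should not be read as losses. The values remain in source records, and no effect on the primary analysis is claimed.

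**What to change.** In Sections 9.7.5 and 9.7.7 only, replace the exclusion with: 'Local results for total bilirubin, ALT, AST, ALP, INR, creatinine and sodium, with the local normal ranges, will be entered in the eCRF and flagged as local.'

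Keep the Section 13.2.2 by-visit statistics on central data. Show the flagged local values, as multiples of the local ULN where applicable, in subject-level hepatic safety listings and in the DMC laboratory listings.

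The cost is one extra eCRF page and some data entry. Local values are less standardised, which the flag and their exclusion from the by-visit statistics deal with. Values already obtained can be entered retrospectively, because both sections require the local report to be available in the source records.
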